7 DERIVED DATA

The following derived data will be calculated and included in the listings:

(1) Baseline value

Baseline value is defined as the last non-missing measurement taken prior to first IMP administration (including unscheduled assessments) (see section [5.1.3](#)).

(2) Duration of subject participation (study exposure)

Study exposure will be calculated as:

Study exposure (days) = last assessment or visit performed – informed consent date +1. It will be then divided by 30.4375 to be presented in months.

(3) Age

Subject age (years) will be as collected in eCRF.

(4) BMI

BMI (kg/m^2) will be derived as $\text{Weight} (\text{kg})/[\text{Height}(\text{cm})/100]^2$ and rounded to the nearest decimal.

(5) Time from diagnosis to screening

Time from diagnosis to screening will be calculated as (date of screening – date of diagnosis). It will be then divided by 30.4375 to be presented in months.

In case of missing screening day, the day will be imputed to 15. In case of missing screening month, the month will not be imputed.

In the same way, in case of missing diagnosis day, the day will be imputed to 15. In case of missing diagnosis month, the month will not be imputed.

No imputation will be performed for missing year.

(6) Compliance

Compliance will be calculated as:

Dose administered divided by dose planned to be administered multiplied by 100. The percentage of residual will be considered to determine the percentage of dose non-administered, and so the dose administered.

A total of two injections will be considered as planned dose administration in this study.

Associated Procedure / Instruction Reference	319480-SOP
Form Reference	080091-FOR v7.0

IPSEN GROUP

CONFIDENTIAL

D-FR-52014-245

SAP Final: Version 1.0: 30 January 2023

PAGE 27/43

(7) Percent change from baseline

Percent change from baseline will be calculated as:

$((\text{assessment at the visit} - \text{assessment at baseline}) / \text{assessment at baseline}) * 100$.

Zero will be used if both assessment at baseline and change from baseline are zero.

(8) Changes from baseline

Changes from baseline will be calculated as a difference from baseline (e.g. assessment at the visit – assessment at baseline).

(9) Study drug exposure

Study drug exposure will be calculated as:

Study drug exposure (days) = last study drug administration date – first study drug administration date +1. It will be then divided by 30.4375 to be presented in months.

(10) Time from first study dose for adverse event

If the start date of the AE is identical to the date of first administration, then “<1” day will be presented.

The time will be calculated as (AE start date – first administration date)+1 and presented in days.

If the AE start date is partial due to missing day, the time from first dose will be presented as a superior inequality (e.g.: for an AE started in FEB2004 after the first administration performed on 31JAN2004, the time from first dose will be as “ ≥ 2 ” days).

If the first administration date is partial due to missing day, the time from first dose will be presented as a superior inequality (e.g. for an AE started on 01FEB2004 after the first administration performed in JAN2004, the time from first dose will be as “ ≥ 2 ” days).

If both the AE start day and the first administration day are missing, the time from first dose will not be presented.

If the AE start month is missing or the first administration month is missing, the time from first dose will not be presented.

If the AE start date is missing or the first administration date is missing, the time from first dose will not be presented.

(11) NCI-CTC AE grades for laboratory parameters

For NCI-CTC gradable laboratory parameters, appropriate grades should be attributed according to the coding rules specified in the NCI-CTCAE version 5.0 if this grade is not present in the database. The grading will be performed based on the laboratory values. CTCAE Grade 0 will be assigned for all non-missing values not graded as 1 or higher.

Associated Procedure / Instruction Reference	319480-SOP
Form Reference	080091-FOR v7.0

IPSEN GROUP

CONFIDENTIAL

D-FR-52014-245

SAP Final: Version 1.0: 30 January 2023

PAGE 28/43

(12) Neutrophils values

In some cases, laboratory data may not be reported as they may be difficult to detect. When the White Blood Cells (WBC) counts are non-missing and recorded as $WBC < 0.5*10^9/L$, the neutrophils value will be imputed as zero in the analysis and CTCAE grade 4 will be assigned.

Associated Procedure / Instruction Reference	319480-SOP
Form Reference	080091-FOR v7.0

IPSEN GROUP

CONFIDENTIAL

D-FR-52014-245

SAP Final: Version 1.0: 30 January 2023

PAGE 29/43

8 CHANGES FROM PROTOCOL

In SAP section 2.1, the hypotheses have been rephrased from Protocol section 9.1: “after 12 months” was updated to “from date of first dose to Day 337” to stick to the protocol endpoints. Twelve months would consider the screening period up to 28 days.

In SAP section 4, the ITT Set was added. The ITT population was mentioned in Protocol section 3 for second estimand while the definition was missed in the protocol. .

The multiple imputation was removed in Protocol Section 3, but it is still present in Protocol Section 1.1 and Section 9.4.2. The multiple imputation will not be used for the statistical analysis considering the new FAS definition and the new estimands definition.

Associated Procedure / Instruction Reference	319480-SOP
Form Reference	080091-FOR v7.0

IPSEN GROUP

CONFIDENTIAL

D-FR-52014-245

SAP Final: Version 1.0: 30 January 2023

PAGE 30/43

10 APPENDICES

Associated Procedure / Instruction Reference	319480-SOP
Form Reference	080091-FOR v7.0

IPSEN GROUP

CONFIDENTIAL

D-FR-52014-245

SAP Final: Version 1.0: 30 January 2023

PAGE 32/43

Appendix 1 List of PCSA Criteria

Associated Procedure / Instruction Reference	319480-SOP
Form Reference	080091-FOR v7.0

IPSEN GROUP

CONFIDENTIAL

D-FR-52014-245

SAP Final: Version 1.0: 30 January 2023

PAGE 33/43

A1. List of PCSA Criteria

PCSA for Vital Signs parameters:

Parameter	PCSA
Systolic Blood Pressure	≤ 90 mmHg and change from baseline ≤ -20 mmHg ≥ 180 mmHg and change from baseline ≥ 20 mmHg
Diastolic Blood Pressure	≤ 50 mmHg and change from baseline ≤ -15 mmHg ≥ 105 mmHg and change from baseline ≥ 15 mmHg
Heart Rate	≤ 50 bpm and change from baseline ≤ -15 bpm ≥ 120 bpm and change from baseline ≥ 15 bpm

PCSA for ECG parameters (source ICH E14):

Parameter	PCSA
QTc	$]450; 480]$ msec $]480; 500]$ msec >500 msec
Delta QTc	$]30;60]$ msec increase from baseline >60 msec increase from baseline

PCSA for Weight from Physical Examination parameters:

Parameter	PCSA
Weight	$\leq -5\%$ change from baseline $\geq 5\%$ change from baseline

Associated Procedure / Instruction Reference	319480-SOP
Form Reference	080091-FOR v7.0

IPSEN GROUP

CONFIDENTIAL

D-FR-52014-245

SAP Final: Version 1.0: 30 January 2023

PAGE 34/43

Appendix 2 Partial/Missing Date Convention

Associated Procedure / Instruction Reference	319480-SOP
Form Reference	080091-FOR v7.0

IPSEN GROUP

CONFIDENTIAL

D-FR-52014-245

SAP Final: Version 1.0: 30 January 2023

PAGE 35/43

A2. Partial/Missing Date Convention

In all listings, missing or incomplete dates should be left as they have been recorded.

Algorithm for Prior/ Concomitant

Medication, non-drug therapies and surgical procedures start and stop dates will be compared to the date of the first IMP administration to allow classification as either Prior only, Prior and Concomitant, or Concomitant only.

In case of partial start and/or stop dates, temporary date imputation will be done to determine the classification and derive the duration of occurrence:

- If a partial start date is reported, the first day of the month will be imputed for missing day and January for missing month,
- If a partial stop date is reported, the last day of the month will be imputed for missing days and December will be imputed for missing month.

In case incomplete start or stop date does not allow the classification, will be classified as concomitant.

The duration of the occurrence will be calculated using the start and end date of the occurrence as end date – start date + 1. In case of partial start or end dates, the duration will be reported as “≤ xx” since at least one date is imputed and maximised.

In case of ongoing occurrence (e.g. at the end of the study or at the time of interim analysis):

- If the start date is complete, the duration will be reported as “≥ xx” and the date of end of study date or last attended visit will be considered as end date.
- If start date is incomplete, the duration is not calculated.

Algorithm for Medical Histories

In case of partial start and/or stop dates, temporary date imputations will be done to determine the duration of occurrence:

- If a partial start date is reported, the first day of the month will be imputed for missing day and January for missing month,
- If a partial stop date is reported, the last day of the month will be imputed for missing days and December will be imputed for missing month.

The duration of the occurrence will be calculated using the start and end date of the occurrence as end date – start date + 1. In case of partial start or end dates, the duration will be reported as “≤ xx” since at least one date is imputed and maximised.

In case of ongoing medical history:

- If the start date is complete, the duration will be “≥ xx” using the screening visit date and the start date of the medical history.
- If start date is incomplete, the duration is not calculated.

Associated Procedure / Instruction Reference	319480-SOP
Form Reference	080091-FOR v7.0

IPSEN GROUP

CONFIDENTIAL

D-FR-52014-245

SAP Final: Version 1.0: 30 January 2023

PAGE 36/43

Algorithm for TEAE

For deriving the TEAE flag the following process of temporary date imputation is done (for AE start date only assuming no AE end date are missing). The date imputation algorithm for incomplete adverse event start dates is described in [Table 2](#). Classification of adverse event according to its treatment-emergent status is then done using the imputed date. The date imputation algorithm for incomplete adverse event end dates is described in [Table 3](#) assuming the latest possible date.

Table 2 Data Imputation Algorithm for Adverse Event Start Date (ASTDT) with first IMP administration on 2002-08-11

Description of incomplete date	Imputed numeric date	Example	
		Character date	Imputed date
Day is missing			
YYYY-MM < YYYY-MM of [First IMP admin.]	YYYY-MM-01	2002-07-XX	2002-07-01
YYYY-MM = YYYY-MM of [First IMP admin.]	Min ([First IMP admin.], AE end date)	2002-08-XX	Min (2002-08-11, AE end date)
YYYY-MM > YYYY-MM of [First IMP admin.]	YYYY-MM-01	2002-09-XX	2002-09-01
Day and month are missing			
YYYY < YYYY OF [First IMP admin.]	YYYY-01-01	2001-XX-XX	2001-01-01
YYYY = YYYY OF [First IMP admin.]	Min ([First IMP admin.], AE end date)	2002-XX-XX	Min (2002-08-11, AE end date)
YYYY > YYYY OF [First IMP admin.]	YYYY-01-01	2003-XX-XX	2003-01-01
Day, month, and year are missing			
XXXX-XX-XX	Min ([First IMP admin.], AE end date)		Min (2002-08-11, AE end date)

Dates are presented using an YYYY-MM-DD format.

YYYY = non-missing year, MM = non-missing month, DD = non-missing day, XX = missing field.

Table 3: Data imputation algorithm for AE end date (AENDT) with last visit/contact date on 2022-02-22 (for AE not ongoing at EoS)

Description of incomplete date	Imputed numeric date	Example	
		Character date	Imputed date
Day is missing			
YYYY-MM < YYYY-MM of [Last visit/contact]	YYYY-MM-31	2021-07-XX	2021-07-31
YYYY-MM = YYYY-MM of [Last visit/contact]	YYYY-MM-22	2022-02-XX	2022-02-22
Day and month are missing			
YYYY < YYYY of [Last visit/contact]	YYYY-12-31	2021-XX-XX	2021-12-31
YYYY = YYYY of [Last visit/contact]	YYYY-02-22	2022-XX-XX	2022-02-22
Day, month, and year are missing (AE not ongoing at EoS)			
XXXX-XX-XX	No imputation	XXXX-XX-XX	

Dates are presented using an YYYY-MM-DD format.

YYYY = non-missing year, MM = non-missing month, DD = non-missing day, XX = missing field.

AEs duration will be calculated using the start and end date of the AE as end date – start date

Associated Procedure / Instruction Reference	319480-SOP
Form Reference	080091-FOR v7.0

IPSEN GROUP

CONFIDENTIAL

D-FR-52014-245

SAP Final: Version 1.0: 30 January 2023

PAGE 37/43

+ 1. In case of partial start/end date the temporary imputed date will be used.

The duration of the AE will be calculated using the start and end date of the AE as end date – start date + 1. In case of partial start or end dates, the duration will be reported as “≤ xx” since at least one date is imputed and maximised.

In case of ongoing AE (e.g. at the end of the study or at the time of interim analysis):

- If the start date is complete, the duration will be reported as “≥ xx” and the date of end of study date or last attended visit will be considered as end date.
- If start date is incomplete, the duration is not calculated.

Associated Procedure / Instruction Reference	319480-SOP
Form Reference	080091-FOR v7.0

IPSEN GROUP

CONFIDENTIAL

D-FR-52014-245

SAP Final: Version 1.0: 30 January 2023

PAGE 38/43

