8.4.1 Time Period and Frequency for Collecting AE and SAE Information

All AEs and SAEs will be collected from the signing of the ICF until EoS at the time points specified in the SoA (Section 1.3).

Medical occurrences that begin before the start of study intervention but after obtaining informed consent will be recorded on the AE section of the case report form.

All SAEs will be recorded and reported to the sponsor or designee immediately and under no circumstance should this exceed 24 hours of awareness of the event, as indicated in

Appendix 10.3. The investigator will submit any updated SAE data to the sponsor within 24 hours of it being available.

Investigators are not obligated to actively seek information on AEs or SAEs after conclusion of the study participation. However, if the investigator learns of any SAE, including a death, at any time after a participant has been discharged from the study, and he/she considers the event to be reasonably related to the study intervention or study participation, the investigator must promptly notify the sponsor.

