5.1.2 Descriptive Statistics

Due to the single-arm nature of the study, all statistical analyses will be descriptive. All raw and derived variables will be listed and described using summary statistics. For categorical variables, summary statistics will be displayed using descriptive statistics by frequency count and percentages by category. The missing category will be presented if applicable. Unless otherwise specified, participants with missing data will be included in the calculation of percentages. For quantitative variables, summary statistics will be displayed using descriptive statistics by number of observations, mean, standard deviation (SD), first quartile, median, third quartile, minimum and maximum. Frequency and proportion of missing data will be displayed.

Associated Procedure / Instruction Reference	319480-SOP
Form Reference	080091-FOR v7.0

For the efficacy analyses, the descriptive statistics of treatment effects and corresponding 95% CIs for the primary endpoint and secondary endpoints will be presented if applicable.

5.1.3 *Baseline Value*

Unless otherwise specified, baseline is defined as the last non-missing measurement taken prior to first Investigational Medicinal Product (IMP) administration (including unscheduled assessments).

5.1.4 *Reference Start Date and Study Day*

Reference start date is defined as the day of the first IMP administration.

The day of the first IMP administration will be Day 1. Study day will be calculated as:

- The difference between the event date and the reference date plus one day, if the event is on or after the reference date.
- The difference between the event date and the reference date, if the date of event is prior to the reference date.

Study day will appear in any listings where an assessment date or event date appears.

In case of partial or missing event date, study day will appear missing while any associated durations will be presented based on the imputations described in [Appendix 2](#).

5.2 **Enrolment, Disposition and Analysis Sets**

A Listing presenting study treatment dispensation details will be provided (Listing 16.1.7).

Following disposition summaries will be provided:

- Summary table with the number and percentage of participants screened, screen failed, reason for screen failures, enrolled, treated, having completed the study, withdrawn and reason for withdrawal,
- Summary table with the number and percentage of participants enrolled per visit,

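### In three of the seven rows of SAP Table 2, the AE duration printed as ≤ xx is not a valid upper bound when onset was before the first injection

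*SAP*

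**What the plan says.** SAP Appendix 2, under the algorithm for TEAE, introduces Table 2 with its purpose: "For deriving the TEAE flag the following process of temporary date imputation is done". The table has seven rows.

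- Four rows cover a recorded month, or a recorded year with no month, that lies before or after that of the first injection. They impute the first day of that month, or 1 January of that year.
- Three rows cover a start in the same month as the first injection, in the same year with the month missing, or with no date at all. They impute "Min ([First IMP admin.], AE end date", that is, the earlier of the two dates.

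Table 3 completes partial end dates at the latest possible date.

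The same appendix then defines duration: "The duration of the AE will be calculated using the start and end date of the AE as end date – start date + 1". For incomplete dates it says "In case of partial start/end date the temporary imputed date will be used", and on reporting: "In case of partial start or end dates, the duration will be reported as “≤ xx” since at least one date is imputed and maximised". An ongoing AE with an incomplete start gets no duration.

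SAP 5.1.4 adds, for partial or missing event dates, that "any associated durations will be presented based on the imputations described in" Appendix 2. Protocol 8.4.1 sets the collection period: "All AEs and SAEs will be collected from the signing of the ICF until EoS". The schedule of activities allows screening up to 28 days before Day 1.

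**The concern.** The ≤ sign is a factual statement: the event lasted no longer than this. It is true only if the start is placed as early, and the end as late, as the recorded information allows. Appendix 2 gives the same justification for medications and medical history. There it is correct, because a missing day becomes the first of the month and a missing month becomes January. For AEs the sentence is attached to a different algorithm.

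The rule in the three rows is sensible for its own purpose. Unless the AE is known to have ended before dosing, it puts the start on the day of the first injection, so that the event counts as treatment-emergent. For duration it removes any pre-dose part of the event. If the AE ended before dosing, start and end coincide and the length is lost altogether. Because AEs are collected from consent, pre-dose onset is an expected case. At stake is the accuracy of AE durations in the safety listings for events recorded around the first injection.

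**Working it through.** **Inputs.** First injection F = 11 August 2002 (the example in Table 2). Imputed start from Table 2. Duration = end − start + 1 (Appendix 2).

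**The table's own examples.** Applying the seven rules gives the start dates that Table 2 prints. July 2002 gives 1 July, September 2002 gives 1 September, 2001 gives 1 January 2001 and 2003 gives 1 January 2003. August 2002, 2002 alone and a fully missing date each give the earlier of 11 August and the AE end date.

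**Printed bound against longest possible duration.**

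| Recorded start | AE end | Imputed start | Printed | Earliest start | Longest possible |
|---|---|---|---|---|---|
| Aug 2002 | 20 Aug | 11 Aug | 20 − 11 + 1 = 10 | 1 Aug | 20 − 1 + 1 = 20 |
| Aug 2002 | 9 Aug | 9 Aug | 9 − 9 + 1 = 1 | 1 Aug | 9 − 1 + 1 = 9 |
| 2002 only | 20 Aug | 11 Aug | 10 | 14 Jul (assumed) | 18 + 20 = 38 |
| 2002 only | 9 Aug | 9 Aug | 1 | 14 Jul (assumed) | 18 + 9 = 27 |
| Jul 2002 | 20 Jul | 1 Jul | 20 | 1 Jul | 20 |
| Jul 2002 | 5 Aug | 1 Jul | 31 + 5 = 36 | 1 Jul | 36 |
| Sep 2002 | 20 Sep | 1 Sep | 20 | 1 Sep | 20 |

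The 14 July start assumes consent 28 days before Day 1 and no AE onset before consent; 14 to 31 July is 18 days. Without that floor, the year-only case ending 20 August could run from 1 January, which is 232 days.

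**General form for the three rows.** Largest possible understatement = min(F, AE end) − earliest compatible start, in days.

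- August 2002, ending 20 August: 11 − 1 = 10 days (20 − 10).
- August 2002, ending 9 August: 9 − 1 = 8 days (9 − 1).
- 2002 only, ending on or after F, with the assumed floor: 28 days (38 − 10).

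When the month is known and the AE ends on or after F, this is the day of the month of the first injection minus 1. It is 0 for dosing on the 1st and at most 30 by the calendar, or at most 28 under the same assumption about consent.

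The last three rows of the table show that the bound is valid where Table 2 uses the first of the month. In particular, an AE with a known July start that ended before dosing prints ≤ 20 or ≤ 36, not ≤ 1.

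**The case against.** The strongest reply is that very little depends on this, and most of that reply stands. SAP 5.8.3 plans no summary of AE duration, and section 7 derives time from first dose for AEs but not duration. The figures would therefore appear only in listings. Appendix 2 leaves incomplete dates there as recorded, so a reader would see the partial start beside the ≤ value.

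A reader might draw four stronger conclusions, which the documents do not support.

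- **That Table 2 generally fails for duration, or that every AE ending before dosing prints ≤ 1.** Four of the seven rows already use the earliest calendar date.
- **That the printed figure is always too short.** It is too low only if onset really preceded the imputed start. An AE recorded as August 2002 that began on or after 11 August is correctly bounded. With a known month and dosing on the 1st, the bound cannot fail.
- **That the TEAE classification is disturbed.** Duration plays no part in it. The flag uses the imputed start date, and SAP 5.8.3 treats undeterminable cases as treatment-emergent.
- **That Table 3 is materially wrong.** Its rule column prints day 31 for any earlier month, which does not exist in five months, and carries the example's day 22 and month 02. But the text above the tables says the latest possible date is assumed, so this is loose notation.

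What the reply does not remove is that, in the three rows, the SAP's stated reason for the ≤ sign is untrue for the start date.

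**Conclusion.** The point holds for three rows of Table 2 and is minor. In those rows the start is not the earliest possible onset, so "since at least one date is imputed and maximised" does not describe it, and the printed bound can be exceeded when the AE began before the first injection. In the SAP's own example the shortfall is up to 10 days for an AE that continues past dosing and up to 8 days for one ending on 9 August. If only the year is known it can reach 28 days for an AE that continues past dosing.

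The year-only figure rests on consent at Day −28 with no earlier onset. Protocol 10.5.1.2 allows longer screening in exceptional COVID-19 cases, and a first injection early in January would cap the shortfall lower. It is also unclear whether a fully missing start counts as partial for the ≤ rule. The documents give no basis for estimating how many AEs would be affected. No endpoint, estimate or AE count changes.

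**What to change.** 1. State that Table 2 applies to the TEAE flag only.
2. For AE duration, impute the earliest date compatible with the recorded partial start: the first day of the recorded month, or 1 January of the recorded year. Use the consent date as a floor only when it falls inside that recorded period. Applied without this condition, the floor would move a start recorded as 2001 to 14 July 2002. For an AE ending 20 August 2002, that would replace a valid bound of 597 days (365 + 232) with 38.
3. For a fully missing start, do not calculate a duration, or print it without the ≤ sign.
4. As a tidy-up, word the Table 3 rules as the last calendar day of the month and the date of the last visit or contact.

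The cost is a sentence or two in Appendix 2, a corrected table and a small change to the listing program. TEAE counts stay as they are.
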